10.3 LABORATORY ASSESSMENTS

Chemistry, hematology, urinalysis and coagulation profile will be assessed at Screening, Week 1 (baseline), Week 12, Week 13, Week 17, Week 21 and Week 25 (see Section 10.4.3 in the clinical trial protocol for a complete list of parameters to be assessed). Summary statistics for these parameters will be presented by visit for the actual value and change from baseline for each test in each laboratory category (hematology, chemistry, urinalysis, and coagulation profile). Shift tables will be presented for

shifts from baseline lab categories to end of study laboratory category. The three laboratory categories will be: L (below lower bound of normal range), N (within normal range), and H (above higher bound of normal range).

The number and percent of subjects experiencing a value greater than 2x and 3x the upper limit of normal (ULN) for ALT and AST will also be presented for each visit and overall (at any visit).

If applicable, a listing will also be provide for all subjects experiencing a value greater than 3x the upper limit of normal (ULN) for ALT or AST and a doubling of baseline total bilirubin occurring on the same visit.

If a lab value is reported using a non-numeric qualifier (e.g., less than (<) a certain value, or greater than (>) a certain value), the given numeric value will be used in the summary statistics, ignoring the non-numeric qualifier.

If a subject has repeated laboratory values for a given time point, the value from the first evaluation at that time point will be used for summarization purposes. For the purpose of determining baseline, the last non-missing observation on or prior to randomization will be used. The Week 25 values will be the last post-baseline value on or prior to Week 25.

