12.4. Analysis of Safety

Exposure will be summarized by treatment group.

Adverse events will be coded by primary system organ class (SOC) and preferred term according to the Medical Dictionary for Regulatory Activities (MedDRA), and summarized by number and percent of subjects in each primary SOC and preferred term. Summaries of these AE subsets will be presented for relationship to trial drug, intensity, seriousness, AEs or SAEs leading to discontinuation and AEs occurring in 5% or greater of any treatment group (by preferred term). Frequencies for deaths and hospitalizations will also be summarized by treatment group and overall.

Data for clinical laboratory tests, ECG, vital signs, and physical and injection site examinations will be summarized using standard descriptive and change from baseline statistics. Shift tables and tabular summaries of abnormalities will be provided, where appropriate.

Medications will be coded using the World Health Organization Drug dictionary and summarized using descriptive statistics.

By-subject listings will be provided for all safety data.

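### Laboratory shift tables use only the last value up to Week 25, so for most analytes no table counts, by arm, subjects who were out of range earlier and returned to normal

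*SAP*

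**What the plan says.** SAP 10.3 schedules chemistry, hematology, urinalysis and coagulation at "Screening, Week 1 (baseline), Week 12, Week 13, Week 17, Week 21 and Week 25". Its shift tables classify each result as low, normal or high, and present "shifts from baseline lab categories to end of study laboratory category". For baseline, "the last non-missing observation on or prior to randomization will be used". For the other end, "The Week 25 values will be the last post-baseline value on or prior to Week 25".

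The same section says "Summary statistics for these parameters will be presented by visit for the actual value and change from baseline for each test". It adds counts of subjects with ALT or AST above 2 and above 3 times the upper limit of normal, at each visit and at any visit. It also adds a listing of subjects with ALT or AST above 3 times that limit and a doubling of bilirubin at the same visit.

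SAP Appendix B lists one shift table each for hematology, chemistry and coagulation (14.4.1.2, 14.4.2.2 and 14.4.3.2), plus Table 14.4.1.3 for ALT, AST and bilirubin doubling. None is described as using the worst post-baseline category.

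Protocol 12.4 states: "Shift tables and tabular summaries of abnormalities will be provided, where appropriate".

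**The concern.** A shift table shows, arm against arm, how many subjects moved out of the normal range. Built on one endpoint value, it answers only how many were out of range at the end. A subject whose platelets, creatinine or lipase left the range at Week 17 and came back by Week 25 is counted as normal to normal.

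The timing matters here because the test arm changes product during the trial. Weeks 12 and 13 close the weekly phase, the first monthly injection is at Week 13, and Weeks 17 and 21 follow the first and second monthly injections. A completer's shift category reflects none of these visits. It reflects Week 25, four weeks after the last scheduled injection. An early leaver contributes an earlier value to the same cells.

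The SAP already counts events at any visit for ALT and AST (10.3) and for QT intervals (10.6). The other analytes have no such count.

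**Working it through.** The plan states no figure to reproduce, so the check applies the table rule to possible results.

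**Inputs.** There are five post-baseline panels, at Weeks 12, 13, 17, 21 and 25 (SAP 10.3; Protocol Tables 3 and 4). The categories are L, N and H (SAP 10.3). The endpoint is the last value on or before Week 25. The SAP does not expressly equate end of study with Week 25, but Protocol Table 4 schedules no panel after it, so that reading is adopted.

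**Step 1: which values can enter.** For a subject with a Week 25 result, only that result enters. For an early leaver, the last available result enters, so an abnormality still present at the last sample does show as a shift.

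**Step 2: patterns for a subject who is N at baseline with all five results.**
- Patterns with at least one abnormal value: 3^5 − 1 = 242.
- Of these, patterns ending in N, shown as N to N: 3^4 − 1 = 80, and 80/242 = 33%.
- Patterns ending in L or H, shown as a shift: 2 × 3^4 = 162, and 162 + 80 = 242.
- With N and H only: (2^4 − 1)/(2^5 − 1) = 15/31 = 48%.

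These are counts of possible sequences, not probabilities. A baseline-to-worst rule would classify all 242 as abnormal.

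**Step 3: an illustration on assumed rates.** The documents give no abnormality rates. Suppose a per-visit rate p and independent visits. The share ever abnormal is 1 − (1 − p)^5, and the share shown as shifted is p.

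| Assumed p | Ever abnormal | Shown as shifted | Difference |
|---|---|---|---|
| 1% | 4.9% | 1% | 3.9 points |
| 5% | 22.6% | 5% | 17.6 points |
| 10% | 41.0% | 10% | 31.0 points |

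If instead every abnormality persisted to the last sample, the difference would be zero. Real results are correlated within subject (Weeks 12 and 13 are only a week apart), so the true difference should be smaller than under independence.

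**Step 4: where else such a value would appear.**
- By-visit statistics include minimum and maximum (SAP 6.0). The most extreme value per arm and visit is shown, but not the number of subjects out of range.
- Listings cover hematology, chemistry and coagulation (SAP Appendix B). They hold the data without a count by arm.
- Adverse event tables by arm (SAP 10.2) include a laboratory finding if it was judged clinically significant (Protocol 10.4.1.1 and 10.4.3).
- The ALT and AST counts cover those two enzymes at their thresholds. Table 14.4.1.3 is titled a shift table, while the SAP text describes its rule as a same-visit listing, so its construction is unclear.

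None of these gives, for the remaining analytes, the number of subjects per arm with a transient out-of-range value not reported as an adverse event.

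**Step 5: the Week 25 row.** Under the rule quoted above, this row combines results observed at Week 25 with earlier results from subjects who left. How much it mixes depends on dropout, for which the documents give no figure.

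**The case against.** The strongest reply is that this is a display choice for descriptive data. SAP 10.0 says no safety outcome is pre-specified and that formal comparisons would be post hoc. Findings that matter clinically have their own route: the investigator marks each flagged value as clinically significant or not, and significant ones are generally expected to be tied to medical history or an adverse event. SAP 10.2 also leaves room for further safety analyses. All of this stands, and it limits the point to a missing count.

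A reader might infer more in four ways, and the documents do not support any of them:
- **That transient abnormalities vanish from the safety report, or that by-visit summaries conceal outliers.** Step 4 shows three routes by which they remain visible, including minimum and maximum.
- **That four fifths of such abnormalities are missed, because one visit in five is used.** That requires every abnormality to last exactly one visit and to be equally likely at each. Neither condition comes from the documents.
- **That the protocol is breached.** Its commitment is qualified by where appropriate, and the liver tables go some way to meeting it.
- **That using the first evaluation at a time point suppresses abnormal repeats.** Protocol 10.4.3 allows extra samples when a result is out of range. In that case the rule keeps the abnormal result and stops a normal repeat from replacing it.

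One further objection shapes the remedy. Unscheduled samples are discretionary, so a worst value that includes them depends on how often each subject was tested, and that may differ by arm.

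**Conclusion.** The point holds in limited form. For analytes other than ALT and AST (with bilirubin doubling), the SAP specifies no table counting, by arm, subjects who were out of range at Week 12, 13, 17 or 21 and normal at the last value. What is lost is mainly the between-arm count of transient abnormalities not reported as adverse events.

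The number of subjects affected cannot be derived from the documents. The 80 of 242 patterns show what the rule cannot display, and the illustration ranges from no loss to the differences tabulated above on assumed rates. The conclusion rests on reading end of study as the last value up to Week 25.

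The point is minor: no primary or hierarchical test is affected. A worst-value table would also not recover an abnormality that arose and resolved between Day 1 and Week 12, because no panel is scheduled in that interval.

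**What to change.** In SAP 10.3 and Appendix B, before unblinding:

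1. Add baseline-to-worst post-baseline shift tables for hematology, chemistry and coagulation, one direction for the lowest value and one for the highest, based on scheduled visits.
2. Include unscheduled and repeat values only in a supplementary version, because testing frequency may differ by arm.
3. Keep the planned shift table, labelled as the last on-treatment value.
4. In the by-visit summary, show values observed at Week 25, without earlier values carried into that row.

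The cost is SAP wording and a few extra tables, with no new data collection. The downside is that more incidental abnormalities will be displayed in both arms.

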8.2. Exclusion Criteria

Subjects will not be eligible to participate in this trial if any one of the following exclusion criteria is met:

1. Current diagnosis of Acquired Immune Deficiency Syndrome (AIDS).
2. Current diagnosis of chronic pain requiring opioids for treatment.
3. Current DSM-V diagnosis of moderate to severe substance use disorder on any other psychoactive substances other than opioids, caffeine or nicotine (e.g., alcohol, cocaine, sedatives) and the non-opioid substance use disorder(s) are considered primary or co-primary, causing current (last 30 days) significant impairment and/or in the judgement of the Investigator would interfere with the efficacy and safety assessments.
4. Pregnant or lactating or planning to become pregnant during the trial.
5. Hypersensitivity or allergy to BPN or other opioids, naloxone or other opioid antagonists, or excipients of CAM2038 or SL BPN.

6. Requires current use of agents that are strong inhibitors or inducers of cytochrome P450 3A4 (CYP3A4) such as some azole antifungals (e.g., ketoconazole), macrolide antibiotics (e.g., clarithromycin), or protease inhibitors (e.g., ritonavir, indinavir, and saquinavir).
7. Subjects with active signs or symptoms of hepatitis and requiring treatment. Subjects with no acute signs of inflammation and no clinical necessity for therapy may be allowed at the discretion of the Investigator.
8. Recent history of or current evidence of suicidal ideation or active suicidal behavior as based on the Columbia Suicide Severity Rating Scale (C-SSRS) (“Yes” responses to questions 4 or 5).
9. Any pending legal action that could prohibit participation or compliance in the trial.
10. Exposure to any investigational drug within the 4 weeks prior to Screening.
11. Participants with a history of risk factors of Torsades de Pointes (e.g., heart failure, hypokalemia, family history of Long QT Syndrome) or an electrocardiogram (ECG) demonstrating a Fridericia's corrected QT interval (QTcF) >450 msec in males and QTcF >470 in females at screening.
12. Aspartate aminotransferase (AST) levels >3 X the upper limit of normal, alanine aminotransferase (ALT) levels >3 X the upper limit of normal, total bilirubin >1.5 X the upper limit of normal, or creatinine >1.5 X upper limit of normal on the Screening laboratory assessments, or other clinically significant laboratory abnormalities, which in the opinion of the Investigator may prevent the subject from safely participating in trial.

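### The SAP's only combined ALT/AST and bilirubin flag needs a same-visit doubling of the subject's own baseline bilirubin, so it is hardest to meet for subjects who enter with raised bilirubin

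*SAP*

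**What the plan says.** SAP 10.3 plans, if applicable, a listing of "all subjects experiencing a value greater than 3x the upper limit of normal (ULN) for ALT or AST" together with "a doubling of baseline total bilirubin occurring on the same visit". Table 14.4.1.3 in SAP Appendix B carries the same baseline-doubling term in its title. Neither place sets a multiple of ULN for bilirubin.

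For laboratory baseline, SAP 10.3 says that "the last non-missing observation on or prior to randomization will be used". Shift tables cover "shifts from baseline lab categories to end of study laboratory category", using three classes (below, within or above the normal range). ALT and AST above 2x and 3x ULN are counted at each visit and over all visits, with no restriction to post-baseline values.

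On entry, Protocol 8.2 criterion 12 excludes "total bilirubin >1.5 X the upper limit of normal" and ALT or AST above 3x ULN, in each case "on the Screening laboratory assessments". Criterion 7 adds, on hepatitis: "Subjects with no acute signs of inflammation and no clinical necessity for therapy may be allowed at the discretion of the Investigator".

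On timing, SAP 10.3 states that the panels "will be assessed at Screening, Week 1 (baseline), Week 12, Week 13, Week 17, Week 21 and Week 25". Protocol Tables 3 and 4 agree.

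**The concern.** The plan judges bilirubin at entry, and ALT and AST on study, in multiples of ULN. Only on-study bilirubin in the combined listing is judged against the subject's own starting value. Where raised baselines are admitted, the absolute level needed for a flag then rises with the baseline. The listing is least sensitive in subjects who already have some hepatic abnormality, and it can pick up subjects whose bilirubin never leaves the normal range.

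I found no other analysis in the SAP or its table list that looks at transaminases and bilirubin together. A clinically notable combination could therefore be absent from the one output built to show it, and an empty listing could be read as more reassuring than it is. No efficacy result is affected.

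**Working it through.** The plan states no figure to reproduce here. The check applies the listing rule to values that entry permits.

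**Inputs**
- Bilirubin rule: at least 2 x own baseline, at the same visit as ALT or AST above 3x ULN (SAP 10.3).
- Highest eligible screening bilirubin: 1.5x ULN (Protocol 8.2, criterion 12).
- Baselines below 1.5x ULN are illustrative; the documents give no distribution.

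**Bilirubin needed for a flag = 2 x baseline (multiples of ULN)**

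| Baseline | Needed | Within normal? |
|---|---|---|
| 0.3 | 2 x 0.3 = 0.6 | yes |
| 0.5 | 2 x 0.5 = 1.0 | yes, at the limit |
| 1.0 | 2 x 1.0 = 2.0 | no |
| 1.5 | 2 x 1.5 = 3.0 | no |

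**Two illustrative subjects**
- Bilirubin 1.4 to 2.7x ULN with ALT 8x ULN: 2.7 / 1.4 = 1.93, below 2, so not flagged. The level needed is 2 x 1.4 = 2.8x ULN.
- Bilirubin 0.3 to 0.6x ULN with ALT moving from 2.9 to 3.1x ULN: 0.6 / 0.3 = 2, so flagged. The ALT condition must also be met; a bilirubin change within normal is not enough alone.

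The 1.5x ULN limit applies to the screening sample, while baseline is normally the Day 1 sample. A subject whose bilirubin rises between the two can have a threshold above 3.0x ULN.

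**Same-visit condition.** Phase 2 panels fall at Weeks 13, 17, 21 and 25, four weeks apart. If ALT exceeds 3x ULN at one draw and bilirubin doubles only at the next, with ALT by then back below the limit, the rule is not met.

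**Shift tables.** The first subject is above normal at baseline and afterwards, so H to H, which is no shift. A rise that has resolved by the last value up to Week 25 is not shown either, because only the end-of-study class is compared with baseline. Repeat values at a time point are also set aside in favour of the first.

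**ALT/AST counts.** Entry allows up to 3x ULN. A subject who enters at 2.5x ULN counts as above 2x ULN without any on-treatment change. The count above 3x ULN is much less exposed, since criterion 12 excludes such values at Screening; only a rise between Screening and Day 1 gets through.

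**Comparison with a fixed cut-off.** Taking 2x ULN purely as an illustration, the fold rise that reaches it is 2 / baseline: 2 / 1.5 = 1.33; 2 / 1.0 = 2; 2 / 0.5 = 4; 2 / 0.3 = 6.67. The two rules coincide only at a baseline of 1.0x ULN, so they complement each other.

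**Detection limit from the schedule.** Day 8 is Week 2, so Week 12 is Day 7 x 11 + 1 = 78. The nominal gap in scheduled chemistry is 78 - 1 = 77 days.

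**The case against.** The strongest answer is that nothing is concealed. SAP 10.3 summarizes actual values and changes by visit for every test, and under SAP 6.0 those summaries include the maximum. Listing 16.2.8.3 prints all chemistry for all subjects. Protocol 10.4.3 has the investigator sign each laboratory report and mark every abnormal value for clinical significance, and Protocol 10.4.1.1 makes clinically significant findings adverse events. The subject with ALT 8x ULN would also be in the ALT count above 3x ULN. All of this stands. A reader might infer that the plan could report no cases when one exists, but the documents do not support that. The output is a descriptive listing, not an adjudicated case count, and SAP 10.0 states that no safety outcome is pre-specified.

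A baseline-relative rule is also defensible where raised baselines are admitted, and a fixed cut-off has its own distortion: 2x ULN is only a 1.33-fold rise from 1.5x ULN. That is a reason to keep the doubling rule and add to it. The over-inclusive case does little harm, since anyone reading the listing can set it aside.

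A reader might also infer that the unrestricted ALT/AST counts hide a difference between arms. Randomization balances pre-existing elevation in expectation, and by-visit counts are planned. Dilution of the count above 2x ULN is possible; concealment is not shown.

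Finally, a reader might treat the Week 12 panel as a duplicate of Week 13 that could be moved into the early gap. The documents do not support calling it a duplicate. Samples go to a central laboratory and the first q4w injection is given at the Week 13 visit, so Week 12 is the last scheduled panel before the visit at which that switch is made. Discretionary samples are also allowed in between (Protocol 10.4.3).

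**Conclusion.** The point holds as a minor weakness in the safety analysis. With the doubling rule alone, the bilirubin level needed for a flag is 3.0x ULN at a baseline of 1.5x ULN and lies within normal at any baseline of 0.5x ULN or less. No other planned analysis flags the combination when bilirubin does not double at the same visit, and the shift tables can miss both worsening within the high class and a transient rise. The underlying values remain available, unflagged.

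The 3.0x ULN figure rests on the entry limit and on reading a doubling as at least twice baseline. The lower baselines and the 2x ULN comparison are assumptions. The documents do not allow an estimate of how many of the roughly 380 subjects would be affected. The absence of scheduled chemistry between Day 1 and Week 12 is noted only as a limit on what any of these summaries can detect.

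**What to change.** Amend SAP 10.3 and Table 14.4.1.3 before database lock and unblinding:

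1. Keep the baseline-doubling flag. Add a second flag for post-baseline ALT or AST above 3x ULN with total bilirubin above a fixed ULN multiple at the same or the next draw. The sponsor should choose and justify the multiple; 2x ULN is used above only as an illustration.
2. Present shift tables from baseline to the worst post-baseline value, including unscheduled draws.
3. Restrict the ALT/AST counts above 2x and 3x ULN to post-baseline values that exceed the subject's own baseline.

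All three use data already planned for collection. They need no protocol change and leave the chemistry schedule, the efficacy analyses and the type I error plan untouched. The cost is extra programming and a somewhat longer listing, including some subjects with raised baselines whose relative rise is small.

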10.4.1.1. Adverse Event Reporting

All AEs must be entered on the AE CRF, regardless of causality or severity. AEs include new AEs, worsening baseline conditions, clinically significant laboratory findings, disease-related signs and symptoms that were not present at baseline, and any events or findings that the Investigator considers clinically significant.

Disease-related signs and symptoms that are present at baseline should not be recorded as AEs unless they worsen in severity or increase in frequency.

Information collected concerning AEs will include the following:

- Name of the event
- Onset date
- Resolution date
- Severity (i.e., mild, moderate, or severe)
- Relationship to trial drug
- Action and outcome
- Seriousness of event

All AEs will be documented and followed from the time the subject has signed the ICF until 14 days after the Follow-up Visit at Week 29 or early termination. SAEs and AEs that have been designated as related to trial drug will be followed until resolution or stabilization.

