10.2 ADVERSE EVENTS

Each AE and serious adverse event (SAE) term recorded on the CRFs will be mapped to a primary system organ class (SOC) and a preferred term using the MedDRA dictionary. The investigator will assess AE severity and relationship to the study treatment.

Columbia Suicide Severity Rating Scale (C-SSRS) will be summarized.

A treatment-emergent adverse event (TEAE) is defined as any AE with an onset date on or after date of randomization, or any ongoing event on the date of first dose that worsens in severity after date of randomization. Only TEAEs with an onset date prior to date of last dose + 30 days will be tabulated in

summary tables. For the purpose calculating treatment emergence and inclusion in summary tables, incomplete onset dates will be imputed as detailed in Appendix A.

TEAEs will be summarized by the number and percent of subjects in each primary SOC and preferred term. Patients will be counted only once for each primary SOC and each preferred term. Summary tables of TEAEs by primary SOC, preferred term and intensity will be provided. If a subject has more than one AE coded to the same preferred term, the subject will be counted only once for that preferred term by using the event with the highest intensity. Similarly, if a subject has more than one AE within a primary SOC category, the subject will be counted only once in that SOC category by using the event with the highest intensity. AEs by primary SOC, preferred term and relationship to study drug will be provided as well. If a subject has more than one AE coded to the same preferred term, the subject will be counted only once for that preferred term by using the most related event. Similarly, if a subject has more than one AE within a primary SOC category, the subject will be counted only once in that primary SOC category by using the most related event. In addition, SAEs by primary SOC and preferred term will be provided. Deaths and SAEs will be summarized similarly to AEs. All TEAE tables will also include the total number of events, counting multiple events per patient.

Injection related AEs, other (non-injection related) AEs as well as all AEs will be presented by treatment group and overall. Summaries of these AE subsets will be presented for the following categories:

- Study drug related
- Intensity
- Relationship to injection
- Possibly study drug related by intensity
- Reasonably injection related by intensity
- Serious

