- AEs which led to discontinuation of treatment
- SAEs which led to discontinuation of treatment
- AEs occurring in 5% or greater of any treatment group (by preferred term)

In the AE summary, preferred terms within each SOC will appear in alphabetical order.

Frequencies for deaths and hospitalizations will also be summarized by treatment group and overall.

To assess the AE profile during the first week of treatment (first week after the randomization), TEAEs that occur within the first week of treatment will be presented.

Other safety analyses will be performed as appropriate

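### The first-value rule for repeated laboratory tests can drop the value that crosses the ALT/AST threshold from the >2x and >3x ULN counts

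*SAP*

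**What the plan says.** SAP 10.3 schedules chemistry at Screening, Week 1 (baseline) and Weeks 12, 13, 17, 21 and 25. Besides summaries of actual values and changes, it plans "The number and percent of subjects experiencing a value greater than 2x and 3x the upper limit of normal (ULN) for ALT and AST"; these "will also be presented for each visit and overall (at any visit").

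For a test repeated at one time point, "the value from the first evaluation at that time point will be used for summarization purposes". Two time points are treated differently. Baseline takes the latest available result up to randomization. For the end of treatment, "The Week 25 values will be the last post-baseline value on or prior to Week 25". No sentence exempts the ALT/AST threshold counts or asks for the highest value.

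A further listing covers subjects with ALT or AST above 3x ULN together with "a doubling of baseline total bilirubin occurring on the same visit"; SAP Appendix B also has a Table 14.4.1.3 on this combination. For adverse events, SAP 10.2 takes the worst case: with several events under one term, "the subject will be counted only once for that preferred term by using the event with the highest intensity".

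**The concern.** Using the first value makes sense for by-visit means and changes from baseline. It gives each subject one value per visit and stops a normal retest from displacing an abnormal first result. It does not suit a count of subjects who crossed a safety threshold, because it can discard the very value that crossed it.

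Repeats are foreseen. Protocol 10.4.3 lets the investigator take extra samples after out-of-range results or when symptoms call for testing. A subject whose first value is raised but still below the threshold is a natural candidate for a recheck, and is also the subject this rule can miss. Protocol 8.2 excludes ALT or AST above 3x ULN at Screening but not lesser elevations. After baseline only five scheduled chemistry time points remain to catch a peak. What is at stake is a possible undercount in a descriptive hepatic safety table.

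**Working it through.** The plan gives no figure to reproduce here. The check applies the SAP 10.3 rules literally to hypothetical subjects and compares the result with a highest-value rule.

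**Inputs**
- Scheduled post-baseline chemistry (SAP 10.3): Weeks 12, 13, 17, 21, 25, so 5 time points.
- Value used: the first at Weeks 12, 13, 17 and 21 (4 of 5); the subject's most recent post-baseline result at Week 25.
- Thresholds k: >2x and >3x ULN.
- Planned arm size: 190 (Protocol 12.5).
- Multiples of ULN below are assumed for illustration; they are not trial data.

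**Conditions for a miss at threshold k**
- By visit (Weeks 12, 13, 17, 21): first value ≤ k and a repeat assigned to that visit > k.
- Overall: the above, every other value in use ≤ k, and the repeat is not the value carried to Week 25.

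The values in use are a subset of all values, so their maximum cannot exceed the overall maximum. At these four visits and overall, the first-value count is therefore never above the highest-value count.

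**Three cases: Week 12 ALT 2.6x first, 4.0x on repeat, threshold >3x**

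| Case | Weeks 13/17/21/25 | Planned rule: Week 12 | Planned rule: overall | Highest value: Week 12 | Highest value: overall |
|---|---|---|---|---|---|
| A | 1.8/1.2/1.0/1.0 | no | no | yes | yes |
| B | 3.4/1.2/1.0/1.0 | no | yes (Week 13) | yes | yes |
| C | none after the repeat | no | yes (4.0 becomes Week 25) | yes | yes |

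The planned rule misses the subject at Week 12 in 3 of 3 cases and overall in 1 of 3. These are illustrations, not frequencies.

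**Further cases that mark the limits**
- Week 17 at 1.8x then 3.4x, other visits at or below 1.2x: missed at Week 17 and overall, for both thresholds.
- Week 17 at 2.4x then 3.4x, other visits at or below 1.2x: counted for >2x; missed for >3x at Week 17 and overall.
- Week 17 at 3.1x then 5.0x: counted under either rule, because the first value already crosses both thresholds.
- Week 25 at 1.9x then 3.3x, both taken by Week 25: counted, because Week 25 takes the last value.

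**Effect on an arm's percentage**, if all 190 are in the safety population: 1/190 = 0.53 points; 2/190 = 1.05; 3/190 = 1.58.

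**The case against.** The strongest reply is that the rule was never meant for these counts. A count of subjects who experience a value, reported overall at any visit, is any-occurrence language, and the first-value sentence can be read as governing only the by-visit descriptive statistics. That reading is possible. But a number-and-percent table is also a summary, and the any-visit wording can equally mean any of the per-visit values already selected. Two defensible readings can give different counts, which is itself a reason to settle the text.

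Second, the trigger is narrow. The repeat must be assigned to the same time point, and SAP 10.3 does not say whether a later unscheduled retest is assigned back to it. A Week 12 recheck may also coincide with the scheduled Week 13 draw. This stands: the point covers only repeats that are assigned to the visit, and their frequency could be zero.

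Third, the information survives elsewhere. Repeats appear in Listing 16.2.8.3, and Protocol 10.4.1.1 says "AEs include new AEs, worsening baseline conditions, clinically significant laboratory findings". SAP 10.2 adds that "Other safety analyses will be performed as appropriate". SAP 10.0 says there is no pre-specified safety outcome, so no formal decision depends on the table. The combined liver output is described in SAP 10.3 as a listing, which the summary rule does not clearly reach. All of this limits the consequence, but none of it corrects the planned table.

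Fourth, the adverse-event rule resolves several events under one term and is not about discretionary retests. That is fair: it shows worst-case logic within the same plan but does not settle the laboratory rule.

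**Conclusion.** The concern holds, as a minor point. Followed as written, SAP 10.3 leaves a higher repeat at Week 12, 13, 17 or 21 out of that visit's >2x or >3x count whenever the first value was at or below the threshold, and sometimes out of the overall count as well. The direction is certain for those counts; the total size is unknown. The 0.53 points per missed subject assumes a safety population of 190 per arm. The conclusion rests on the literal reading of the first-value sentence and on the repeat being assigned to the earlier visit. It touches descriptive safety counts only.

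**What to change.** Limit the first-evaluation rule in SAP 10.3 to by-visit descriptive statistics (actual value and change from baseline), and add text to this effect:

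- For the ALT/AST >2x and >3x ULN counts, each visit uses the highest value assigned to it, repeats included.
- The overall count uses the highest of all post-baseline values, including repeat and unscheduled samples.
- A subject with no Week 25 sample keeps the existing last-value rule for that visit.
- The combined ALT/AST and bilirubin output (the listing and Table 14.4.1.3) considers all values, repeats included, and still requires both findings at the same visit.
- The rule for assigning unscheduled retests to visits is stated.

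The highest-value rule still prevents a normal retest from hiding an abnormal first value. The cost is a few sentences before database lock and minor programming; no new samples are needed. One small drawback is that subjects retested more often, at the investigator's discretion, have slightly more chance of crossing a threshold.
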